8.7. Observation Period

Observation period: The observation period will be 52 weeks for patients not undergoing HSCT within 52 weeks after the start of BESPONSA treatment or until 52 weeks following HSCT for patients undergoing it within 52 weeks after the start of BESPONSA treatment. For a patient starting BESPONSA treatment before 30 April 2020 who is transferred to another hospital during the observation period, the conclusion of the agreement on the implementation of this investigation should be requested to the hospital to which the patient has been transferred, and data from there should be collected to the extent possible.

(1) Treatment phase

From treatment initiation to Day 28 post-treatment: Safety (e.g., AEs) and efficacy (hematologic remission and survival)

(2) Follow-up phase

From Day 29 post-treatment to Week 52 (patients who did not undergo HSCT before Week 52) or 52 weeks after HSCT (patients who underwent HSCT before Week 52): Safety (VOD/SOS) and efficacy (survival)

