## 2.1. Study Design

- **Target population**

*All patients who received this drug will be included in this survey.*

- **Survey period**

*The scheduled periods of this survey are as follows:*

*Survey period: From the date of launch of this drug to 5 years\**

*Registration period: From the date of launch of this drug to the time of lifting of approval conditions for all-case survey\**

*\*: Patients who started to receive this drug on or after May 1, 2020 will only be registered.*

The protocol may be changed to terminate the registration only period, but this change will not affect the SAP.

- **Observation period**

*Observation period: The observation period is to be 52 weeks for patients who did not undergo hematopoietic stem cell transplant (HSCT) within 52 weeks after the start of the treatment with this drug and up to 52 weeks after HSCT for patients who underwent HSCT within 52 weeks after the start of this drug. If patients who started to receive this drug on or before April 30, 2020 are transferred to another hospital during the observation period, the transferred hospitals will be requested to conclude a contract for the conduct of this survey, and the information at the transferred hospitals will be collected as much as possible.*

*[1] Treatment Period*

*From the start of treatment to Day 28 post-final dose: For assessments of safety (e.g., adverse events) and effectiveness (hematologic response, survival time)*

*[2] Follow-up period*

*For 52 weeks from 29 days after the final dose (for patients who did not undergo HSCT by 52 weeks after the start of treatment) or for 52 weeks after HSCT (for patients who underwent HSCT by 52 weeks after the start of treatment): For assessments of safety (VOD/SOS) and effectiveness (survival time)*

The starting point for the 52 week follow-up after HSCT is the day of the last HSCT performed within 52 weeks after the start of this drug.

- **Safety specification**

See Protocol Section 7.1.

- **Sample size and its rationale**

*Of the patients who have received this drug, a total of 176 patients with relapsed or refractory CD22 positive (CD22+) acute lymphocytic leukemia (ALL) will be included in the safety analysis set. In consideration of dropouts during the survey, 200 patients will be registered.*

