#### 8.1.4. Time-to-event data

For time-to-event data, the median, 1st quartile, and 3rd quartile will be determined using the Kaplan-Meier method. The rate at each time point will also be determined. To estimate CIs, log-log transformation will be used (this corresponds to specifying loglog under the conftype option in the proc lifetest statement of the SAS® lifetest procedure). In addition, Kaplan-Meier plots will be presented.

When time data are compared between subgroups using the Kaplan-Meier method, the hazard ratio of event occurrence and its 95% CI will be determined using the Cox proportional hazards model (ties handled by the Breslow method). In addition, the hazard ratio and its 95% CI will be presented graphically.

In the analysis of time data with competing risks, the cumulative incidence rate at each time point that takes into account competing risks will be determined (this corresponds to using the event code option in the time statement of the SAS® lifetime procedure). The standard error is to be estimated by the delta method. In addition, the time course of cumulative incidence will be graphically presented.

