#### **8.2.4.4. Overall survival**

Percentages of deaths and their causes of death will be summarized as per Section 8.1.2.

Overall survival (OS) will be analyzed using the entire analysis set and also by HSCT performed or not performed after the start of this drug, as per Section 8.1.4. Those who included in the analysis are patients in the EAS who finished the survey (Patients who are recorded as discontinued in the "Record of continued/discontinued survey [treatment period]" in the case report form or patients for whom "Record of continued/discontinued survey [follow-up period]" in case report form is filled in. The latter means the survey is discontinued and completed for the patient.). The time points for rate estimation will be at Months 3, 6, 9, and 12 for the entire analysis set and patients who did not undergo HSCT, and at Months 3, 6, 9, 12, 18, and 24 for patients who underwent HSCT. Results of the analysis for the entire analysis set should be interpreted with caution, because the planned observation period for this survey differs for patients who did and did not undergo HSCT after the start of this drug (see Section 2.1).

The OS after the final dose of this drug in patients who underwent HSCT will also be analyzed in the same manner. Those who included in the analysis are patients in the EAS who underwent HSCT after the start of this drug and finished the survey (Patients who are recorded as discontinued in the "Record of continued/discontinued survey [treatment period]" in the case report form or patients for whom "Record of

continued/discontinued survey [follow-up period]" in case report form is filled in. The latter means the survey is discontinued and completed for the patient.).

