#### 8.2.4.5. Subgroup analyses

Subgroup analyses for hematologic response and MRD will be performed by each of the factors defined in Section 5.4. In addition, hematological response rate ratio and MRD negative rate ratio (corresponds to risk ratio in the SAS) for different subgroups will be determined as per Section 8.1.3, and presented graphically. If, however, there is a category with less than 10 patients and after reconsideration it is considered difficult to determine the ratios for the category, it will not be determined for the each of the relevant category.

In addition, subgroup analyses of OS will also be performed for each of the factors defined in Section 5.4. Hazard ratios for the occurrence of events for different subgroups will be determined as per Section 8.1.4 and graphically presented. If, however, there is a category with less than 10 patients and after reconsideration it is considered difficult to determine the hazard ratio for the category, it will not be determined for the relevant category. The OS after the final dose of this drug in patients who underwent HSCT will also be analyzed in the same manner. Results of the analysis for the entire analysis set should be interpreted with caution, because the planned observation period for this survey differs for patients who did and did not undergo HSCT after the start of this drug (see Section 2.1). The above subgroup analyses of OS will also be performed by HSCT performed or not performed after the start of this drug.

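### Entire-set overall survival has no Week 52 limit on its curve, quantiles or hazard ratios, although only HSCT recipients are planned to be followed beyond that point

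*SAP*

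**What the plan says.** **Observation.** Protocol 8.7 states: "The observation period will be 52 weeks for patients not undergoing HSCT within 52 weeks after the start of BESPONSA treatment". SAP 2.1 repeats this, and follows recipients "up to 52 weeks after HSCT for patients who underwent HSCT within 52 weeks after the start of this drug". It adds: "The starting point for the 52 week follow-up after HSCT is the day of the last HSCT performed within 52 weeks". A recipient can therefore be observed for up to about 52 + 52 = 104 weeks.

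**Conflicting wording.** Item [2] of SAP 2.1 counts the non-recipients' 52 weeks from 29 days after the last dose, which taken literally runs past Week 52. The matching item in Protocol 8.7 reads "From Day 29 post-treatment to Week 52 (patients who did not undergo HSCT before Week 52) or 52 weeks after HSCT".

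**Analysis.** SAP 6.2 censors OS at the date the patient was last confirmed alive, with no cut-off. Under SAP 8.1.4, "the median, 1st quartile, and 3rd quartile will be determined using the Kaplan-Meier method", together with a plot and, for subgroup comparisons, Cox hazard ratios. No time limit is given for any of these. SAP 8.2.4.4 applies this to the entire set and by HSCT status.

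**Safeguards.** Entire-set rates stop at Month 12, and Months 18 and 24 are tabulated for recipients only. The entire-set result carries the warning "Results of the analysis for the entire analysis set should be interpreted with caution, because the planned observation period for this survey differs". SAP 8.2.4.5 repeats the warning for subgroups and adds: "The above subgroup analyses of OS will also be performed by HSCT performed or not performed after the start of this drug".

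**The concern.** Whether a patient is still observed after Week 52 depends on HSCT, an event after baseline that may be related to survival. SAP 6.4 lists HSCT status among potential prognostic factors for OS, without saying whether HSCT before or after the drug is meant. The Kaplan-Meier method treats patients censored at Week 52 as having the same later survival as those who stay under observation, and here those who stay are all recipients.

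OS is one of the two main efficacy endpoints in Protocol 8.12.2.2. An entire-set plot that runs on towards Month 24, or a quartile falling after Week 52, would be read as describing everyone treated. The entire-set hazard ratios would likewise join a comparison in the whole cohort up to Week 52 to a comparison among recipients afterwards. The Month 12 stop is applied to the rates but not to these other outputs from the same data.

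**Working it through.** **Inputs.** The documents give no OS figure, HSCT share or hazard. Their one design calculation, 80.4% power for VOD/SOS with 176 patients, reproduces (88 per group, 18.45% against 6.15%, two-sided 0.1) but does not bear on OS. The following are therefore assumptions: 26-55% of patients transplanted, exponential survival, a non-recipient median of 5 to 9 months, and a post-HSCT median from the same value up to 24 months. Each scenario was simulated with 176 patients and 400 replicates. Non-recipients were censored at Day 364 and recipients at HSCT + 364 days, and the result was compared with full follow-up of the same patients.

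**Step 1: who is at risk.** In every scenario all patients at risk after Day 364 were recipients (17 to 79 of 176).

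**Step 2: what the curve estimates.** Let S52 be cohort survival at Week 52, w the recipients' share of those alive then, and C_R and C_N the later conditional survival of recipients and non-recipients.

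- Planned curve: S52 × C_R
- Cohort survival: S52 × [w × C_R + (1 − w) × C_N]
- Difference: S52 × (1 − w) × (C_R − C_N)

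The sign follows C_R − C_N. The level still carries the whole cohort's S52; only the later decline comes from recipients alone.

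**Step 3: one case by hand.** Take medians of 7 months (non-recipients) and 24 months (after HSCT), with 31% transplanted. The simulation gave S52 = 0.403 and 45 of 176 recipients at risk, so w = (45/176)/0.403 = 0.635. Week 52 is 364/30.44 = 11.96 months, leaving 6.04 months to Month 18.

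- C_R = 2^(−6.04/24) = 0.840; C_N = 2^(−6.04/7) = 0.550
- Planned: 0.403 × 0.840 = 0.339 (simulated 0.340)
- Cohort: 0.403 × (0.635 × 0.840 + 0.365 × 0.550) = 0.296 (simulated 0.295)

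**Step 4: range at 18 months (simulated).**

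| Medians, non-recipient / post-HSCT (months) | Transplanted | Planned | Full follow-up |
|---|---|---|---|
| 9 / 9 | 35% | 0.250 | 0.250 |
| 7 / 7 | 31% | 0.173 | 0.170 |
| 7 / 12 | 31% | 0.253 | 0.227 |
| 7 / 24 | 31% | 0.340 | 0.295 |
| 7 / 24 | 50% | 0.389 | 0.375 |

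With a lower hazard in recipients, the excess over all scenarios was about 1 to 4.5 points. A post-HSCT median of 30 months, in a large-sample calculation (9/30, 30% transplanted), gave 0.476 against 0.417 at 17.0 months, about 6 points. A run with a higher hazard in recipients gave 0.271 against 0.299, so the bias reverses.

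**Step 5: quantiles.** A quantile is affected only if it falls after Week 52.

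- Third quartile, S52 about 0.19 (5/5): 9.9 against 9.9 months, unaffected.
- Third quartile, S52 above 25%: 18.3 against 16.5 months (7/12, 31%); 18.6 against 15.2 (5/24, 26%); not reached against 21.1 (7/24, 31%).
- Median, S52 = 0.534 (9/30, 30%): 14.8 against 13.3 months.

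**Step 6: hazard ratios.** One simulation (0.02 per week without HSCT, 0.008 after) gave 1.18 and 1.13 for a baseline factor with and without the follow-up after Week 52: 1.18/1.13 = 1.04. Shifts ran up to about 5%.

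**Step 7: effect of a Week 52 cut.** Estimates up to Day 364 were unchanged in every scenario. The third quartile was reached by Week 52 in 99% of replicates at S52 about 0.19, in 34% at about 0.27, in about 6% at about 0.30, and in at most 0.25% at 0.36 or above.

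**The case against.** The SAP has seen the problem and dealt with much of it. It tabulates no entire-set rate after Month 12, gives later rates for recipients only, repeats OS and its subgroup analyses by HSCT status, and states the caution twice. Testing is exploratory (SAP 4.1) and the study was sized for VOD/SOS. The hazard-ratio shift is small against sampling error: assuming about 105 deaths and a balanced factor, the standard error of the log hazard ratio is 2/√105 = 0.195, a 95% interval of roughly ×/÷ 1.47. The cut also does not recover a late third quartile. In the 7/24 case at 31% transplanted it is not reached either way.

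All of this stands, and it keeps the point modest. It does not close it. The caution does not say where the curve stops representing the cohort, and the Month 12 limit does not reach the plot, the quantiles or the Cox models. The split by HSCT status is not a substitute for a cohort curve, because it groups patients from drug start by something that happens later.

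A reader might go further and infer that the entire-set results are simply too favourable, that the tail describes recipients only, or that the plan uses all follow-up throughout. The documents support none of these. They give no hazards, so the direction is unknown. The tail starts from the whole cohort's Week 52 survival. The tabulated entire-set rates do stop at Month 12.

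**Conclusion.** The point holds as a gap in specification that is cheap to close. Under Protocol 8.7 and the main sentence of SAP 2.1, entire-set OS after Week 52 rests on recipients alone, and nothing limits the curve, the quantiles or the Cox models to the period when the whole cohort is observed.

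The bias depends on the difference in hazard after Week 52 between recipients and surviving non-recipients. A lower hazard in recipients is plausible and gives about 1 to 5 points too high at 18 months under most of the assumptions tried. Equal hazards give none, and a higher one gives a curve that is too low. The third quartile is exposed only if Week 52 survival exceeds 25%, and the median only if it exceeds 50%. Hazard ratios change little, and that figure rests on a single simulation.

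The statement that only recipients are followed past Week 52 also depends on how item [2] of SAP 2.1 is resolved. A survival confirmation for a non-recipient dated after Week 52 would count under SAP 6.2.

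**What to change.** In SAP 8.2.4.4 and 8.2.4.5, administratively censor every patient at Week 52 for the entire-set OS curve, median, quartiles and Cox models. Report survival beyond Week 52 only within HSCT recipients.

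Define the cut so that the Month 12 rate can still be estimated. The SAP gives OS in months without a conversion from days; if 12 months means about 365 days, a cut at Day 364 falls just short of it. Either tabulate the last entire-set rate at Week 52 or define Month 12 as the day of the cut.

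Reconcile item [2] of SAP 2.1 with the observation period stated just above it and with Protocol 8.7. The Week 52 cut works under either reading.

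The cost is one sentence in each section and one line of code. Deaths after Week 52 drop out of the entire-set hazard ratios but stay in the recipient analyses. Any quantile not reached by Week 52 is reported as not reached, which for the third quartile is likely whenever Week 52 survival is clearly above 25%.

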#### 8.2.4.5. Subgroup analyses

Subgroup analyses for hematologic response and MRD will be performed by each of the factors defined in Section 5.4. In addition, hematological response rate ratio and MRD negative rate ratio (corresponds to risk ratio in the SAS) for different subgroups will be determined as per Section 8.1.3, and presented graphically. If, however, there is a category with less than 10 patients and after reconsideration it is considered difficult to determine the ratios for the category, it will not be determined for the each of the relevant category.

In addition, subgroup analyses of OS will also be performed for each of the factors defined in Section 5.4. Hazard ratios for the occurrence of events for different subgroups will be determined as per Section 8.1.4 and graphically presented. If, however, there is a category with less than 10 patients and after reconsideration it is considered difficult to determine the hazard ratio for the category, it will not be determined for the relevant category. The OS after the final dose of this drug in patients who underwent HSCT will also be analyzed in the same manner. Results of the analysis for the entire analysis set should be interpreted with caution, because the planned observation period for this survey differs for patients who did and did not undergo HSCT after the start of this drug (see Section 2.1). The above subgroup analyses of OS will also be performed by HSCT performed or not performed after the start of this drug.

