8.8.11. Clinical Evaluation

8.8.11.1. Hematologic Remission

Response will be assessed according to the following response criteria, and the best overall response during the observation period will be entered. However, if subsequent treatment for the target disease is started or HSCT is performed, the best overall response before the start of the subsequent treatment or HSCT, whichever is earlier, will be entered.

Response criteria

1. CR
 - No peripheral blasts or extramedullary disease (no lymphadenopathy, splenomegaly, or skin/gum infiltration/testicular mass/CNS involvement)
 - Trilineage hematopoiesis (TLH) and <5% blasts
 - Absolute neutrophil count (ANC) >1,000/ μ L
 - Platelets >100,000/ μ L
 - No recurrence for 4 weeks
2. CRi (CR with incomplete count recovery)
 - Recovery of platelets but <100,000/ μ L or ANC is <1,000/ μ L
3. Progressive disease (PD)
 - Increase of at least 25% in the absolute number of peripheral blood or bone marrow blasts or development of extramedullary disease
4. Relapsed disease
 - Reappearance of blasts in the blood or bone marrow (>5%) or in any extramedullary site after CR
5. Inevaluable

Inotuzumab

B1931024 NON-INTERVENTIONAL STUDY PROTOCOL

Amended 8, 12 December 2023

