8.8.11.2. Minimal Residual Disease (MRD)

If a MRD test gives a negative result during the observation period, the earliest date will be entered. However, if subsequent treatment for the target disease is started or HSCT is performed, MRD will be assessed before the start of the subsequent treatment or HSCT, whichever is earlier.

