- Peripheral blast count immediately before the start of this drug [ $\leq 1000/\mu\text{L}$ ,  $> 1000/\mu\text{L}$ , not performed]
- Myeloblast count immediately before the start of this drug [ $\leq 50\%$ ,  $> 50\%$ , not performed]
- Salvage line of the induction treatment with this drug [Initial induction, 1st, 2nd, 3rd or later]
- HSCT before the start of this drug [not performed, performed]
- Pregnancy [absent, present] \* Pregnancy during the treatment period. Limited to cases in which information on pregnancy is collected

Subgroup analyses of overall survival (OS) will be performed for the following patient characteristics and other factors:

- Age [ $< 15$  years,  $\geq 15$  to  $< 65$  years,  $\geq 65$  years]
- Age [ $< 18$  years,  $\geq 18$  to  $< 55$  years,  $\geq 55$  years]
- Age [ $< 15$  years,  $\geq 15$  to  $< 40$  years,  $\geq 40$  years]
- Disease name [Relapsed CD22+ acute lymphocytic leukemia (ALL), refractory CD22+ ALL]
- Chromosome karyotype [normal, t (4;11), unknown]
- Chromosome karyotype [Philadelphia chromosome positive, negative, unknown]\* Philadelphia chromosome is considered positive if the chromosome karyotype is t(9;22).
- Hemoglobin level immediately before the start of this drug [ $< 10\text{ g/dL}$ ,  $\geq 10\text{ g/dL}$ , not performed]
- Platelet count immediately before the start of this drug [ $< 10 \times 10^4/\mu\text{L}$ ,  $\geq 10 \times 10^4/\mu\text{L}$ , not performed]
- Peripheral blast count immediately before the start of this drug [ $\leq 1000/\mu\text{L}$ ,  $> 1000/\mu\text{L}$ , not performed]
- Myeloblast count immediately before the start of this drug [ $\leq 50\%$ ,  $> 50\%$ , not performed]
- Salvage line of the induction treatment with this drug [Initial induction, 1st, 2nd, 3rd or later]
- HSCT before the start of this drug [not performed, performed]
- Pregnancy [absent, present] \* Pregnancy during the treatment period. Limited to cases in which information on pregnancy is collected
- Best overall response [CR or CRi, progression or relapse, indeterminate or other, not performed]
- Best overall response [CR, CRi]\* "Progression", "relapse", "indeterminate/other" and "not performed" are excluded.
- MRD [negativity achieved, negativity not achieved, test not performed] \* Irrespective of the result of best overall response.

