#### 6.2. Effectiveness Endpoints

- Hematologic response. This is assessed as one of the following categories based on the best overall hematologic response: CR, CRi, progressive disease (PD), relapse, indeterminate, other, assessment not performed. "Other" corresponds to the cases where the clinical assessment of hematologic response was performed but the result did not fall into any of the categories described in the case report form, while "assessment not performed" corresponds to the cases where the clinical assessment was not performed.
- MRD. This is assessed as one of the following categories based on the MRD status: negativity achieved, negativity not achieved, unknown, test not performed.
- Overall survival:
  - Overall survival: Defined as the months from the start of this drug to all-cause death.
  - Event: Death
  - Censoring: The patient is confirmed alive at the time of completion or discontinuation of the survey. The endpoint will be censored on the day when patient's survival was last confirmed.
- Overall survival after the final dose of this drug in patients who underwent HSCT:
  - Overall survival: Defined as the months from the date of final dose of this drug to all-cause death.
  - Event: Death
  - Censoring: The patient is confirmed alive at the time of completion or discontinuation of the survey. The endpoint will be censored on the day when patient's survival was last confirmed.

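### Cox hazard ratios for OS counted from drug start use MRD and response status reached later, which biases the MRD comparison and some of the response comparisons

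*SAP*

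**What the plan says.** **OS clock.** SAP 6.2 measures OS as follows: "Defined as the months from the start of this drug to all-cause death".

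**OS subgroup factors.** The OS list in SAP 5.4 includes "Best overall response [CR or CRi, progression or relapse, indeterminate or other, not performed", "Best overall response [CR, CRi" and "MRD [negativity achieved, negativity not achieved, test not performed", each closed by a bracket in the original, plus a factor crossing response with MRD. SAP 8.2.4.5 covers the whole list: "In addition, subgroup analyses of OS will also be performed for each of the factors defined in Section 5.4". It asks for hazard ratios for these subgroups and graphs them. The model is the ordinary Cox model of SAP 8.1.4.

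**When status is fixed.** Protocol 8.8.11.1 takes the best response over the observation period, stopping at subsequent treatment or HSCT. The CR criteria include "No recurrence for 4 weeks". For MRD, Protocol 8.8.11.2 says: "If a MRD test gives a negative result during the observation period, the earliest date will be entered", with the same stopping rule. SAP 8.2.4.1 allows a first CR or CRi from Cycle 1 to beyond Cycle 6, or after treatment.

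**Safeguards.** The SAP plans no landmark, time-dependent covariate or later time origin for these factors. The one caution in SAP 8.2.4.5 concerns the different observation periods with and without HSCT. SAP 4.1 calls all testing exploratory.

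**The concern.** To be classed as achieving MRD negativity or remission, a patient must live to the assessment that shows it. A patient who dies first cannot join that group. A Cox model with the final status as a fixed covariate treats the achieved group as at risk from Day 0, although by construction its members could not die before qualifying. The resulting hazard ratio departs from 1 even when the status has no bearing on survival.

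The not-performed level does not solve this, because it takes only patients who were never assessed. SAP 6.2 places a patient who was assessed but fits no listed response category under *other*. If that patient dies before the next assessment, the death counts there; with longer survival the patient might have become a responder.

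OS is one of the two main efficacy endpoints (Protocol 8.12.2.2), and SAP 6.4 lists response and MRD as potential prognostic factors for it. A reader of the graphed hazard ratios could take an artefact for prognostic evidence.

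**Working it through.** The documents state no figure for OS, response timing or these subgroups, so there is nothing of the plan's own to reproduce. The power of 80.4% concerns VOD/SOS risk factors and has no bearing here.

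**Assumptions, none from the documents**
- OS is exponential with a median of 5 or 10 months and is unrelated to response or MRD, so the true HR is 1.
- Assessments fall on Days 28, 56 and 84, in line with the roughly 28-day cycles in Protocol 8.2.
- The chance *p* of first achieving the status is 20%, 35% or 50% at each assessment.
- Follow-up ends at 364 days, and a month is 30.44 days.

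**Month 3 gap, exactly.** Let S(d) = 2^(−d/median in days) and S₃ = 2^(−3/median in months).
- Share achieving: A = p·S(28) + (1−p)p·S(56) + (1−p)²p·S(84)
- Share assessed but never achieving: N = S(28) − A
- Month 3 OS if achieved: S₃[1−(1−p)³]/A
- Month 3 OS if never achieved: S₃(1−p)³/N

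Median 5 months, p = 0.5:
- S(28), S(56), S(84) = 0.880, 0.775, 0.682, and S₃ = 0.660.
- A = 0.440 + 0.194 + 0.085 = 0.719, and N = 0.880 − 0.719 = 0.161.
- Month 3 OS is 0.660 × 0.875/0.719 = 80.3% against 0.660 × 0.125/0.161 = 51.2%, a gap of 29 points.

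Median 10 months, p = 0.2:
- S(28), S(56), S(84) = 0.938, 0.880, 0.826, and S₃ = 0.812.
- A = 0.188 + 0.141 + 0.106 = 0.434, and N = 0.504.
- Month 3 OS is 91.3% against 82.5%, a gap of 9 points.

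**Cox HR.** This is simulated with 1,000,000 patients per row, for assessed patients who never achieve versus those who achieve:

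| Median OS | p | HR from drug start | Month 3 gap (points) |
|---|---|---|---|
| 5 months | 0.20 | 1.25 | 15 |
| 5 months | 0.35 | 1.38 | 20 |
| 5 months | 0.50 | 1.64 | 29 |
| 10 months | 0.20 | 1.20 | 9 |
| 10 months | 0.35 | 1.30 | 13 |
| 10 months | 0.50 | 1.51 | 20 |

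A smaller simulation of the same inputs gave HR 1.17 to 1.60 and gaps of 8 to 28 points. From a Day 84 landmark the HR was 0.97 to 1.02.

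**MRD achieved versus not achieved among tested patients.** A separate null simulation assumed median OS of 4 to 12 months and serial tests with a 25 to 40% chance of negativity at each. It gave HR 0.67 to 0.77, or 1.30 to 1.49 when inverted (1/0.77 and 1/0.67).

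**CR/CRi versus progression or relapse.** A patient must also be alive to be recorded as progressing.
- With both recorded at the same visits, the null HR is 0.98 to 1.03.
- In a separate set of runs (median OS 4 to 12 months), the HR for CR/CRi versus progression was 0.91 to 0.94 if progression is recorded earlier than response, and 1.21 to 1.32 if later.

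**CR versus CRi.** If CR alone needs 28 further days, the null HR for CRi versus CR is about 1.07 to 1.18. If CRi carries the same rule, this source of bias disappears.

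**The case against.** **The best-response factor has four levels and no pooled non-responder group.** This stands. The 1.2 to 1.6 range cannot be read as the bias in CR/CRi versus progression or relapse, where timing decides the sign. It fits MRD achieved versus not achieved. For response it is only a guide to the comparison with indeterminate/other, where SAP 6.2 puts assessed patients outside the listed categories. The reference levels were underlined in SAP 5.4, and that underlining is lost in the text available here, so the exact contrasts to be reported are not known.

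**CR versus CRi depends on one reading of Protocol 8.8.11.1.** This stands. CRi is described as CR with incomplete count recovery, and only the count exception is listed. It may well inherit the other CR criteria, including the 4 weeks without recurrence.

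**The analyses are exploratory, in a single-arm safety survey.** This lowers the severity: no decision rule or sample size rests on these ratios. It does not remove the bias, because the label concerns p-values and error control while the estimates and intervals are still graphed.

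**Some mitigation exists.** Classification stops at subsequent treatment or HSCT, which shortens the window. OS from the final dose in HSCT patients is less exposed, since all of them survived to transplant and were classified before it. Neither point corrects the main analysis from drug start.

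**Conclusion.** The concern holds for MRD negativity achieved versus not achieved, including that contrast within CR/CRi in the combined factor. It also holds for CR/CRi versus the levels that collect early deaths. Under the assumptions above, the artefact alone is worth an HR of about 1.2 to 1.6 for assessed patients who never achieve the status versus those who do, and about 9 to 29 points of Month 3 OS. Both figures would move with the true survival and response timing, which the documents do not give.

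A reader might infer that every planned response hazard ratio favours response, or that the survival advantage shown would be wholly artefact. The documents support neither. The contrast with progression or relapse may be unbiased or reversed, the CR versus CRi contrast turns on an unclear definition, and a real prognostic effect may coexist with the bias.

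Severity is should-fix, because these are exploratory efficacy subgroups in a safety survey.

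**What to change.** In SAP 8.2.4.5, for best overall response, CR versus CRi, MRD, and response combined with MRD:

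- Replace the drug-start hazard ratios with a Cox model that uses the first CR/CRi date and the earliest MRD-negative date as time-dependent covariates. Alternatively, pre-specify a landmark such as Day 84: classify by status reached by then, and count OS from then among patients still alive.
- Keep any drug-start curves by response or MRD as descriptive, without hazard ratios, and state why.
- State whether the 4-week rule applies to CRi.

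The dates appear to be available. SAP 8.2.4.1 uses the assessment date of CR or CRi to find the first cycle of remission, and Protocol 8.8.11.2 records the earliest negative MRD date. Before programming, confirm that the response date held is that of first CR/CRi and not only that of best response.

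The cost is a short SAP edit and modest programming. A Day 84 landmark drops patients who die before it: 1 − S(84) = 1 − 0.826 = 17% at a median of 10 months and 1 − 0.682 = 32% at 5 months. The time-dependent model avoids that loss.
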